5.4. Safety Variables

This trial is using the DSS system that is classified as a device. Therefore we will provide safety reporting on the following for the DSS arm only:

1. Adverse Device Effects (ADE): Any untoward and unintended response to a medical device.
 - This definition includes any event resulting from insufficiencies or inadequacies in the instructions for use or the deployment of the device.
2. Serious Adverse Device Effects (SADE): Adverse device effect that has resulted in any of the consequences characteristic of a serious adverse event or that might have led to any of these consequences if suitable action had not been taken or intervention had not been made or if circumstances had been less opportune.
 - Unanticipated Serious Adverse Device Effect (USADE): Any serious adverse device effect which, by its nature, incidence, severity or outcome, has not been identified in the anticipated AE's
 - Anticipated Serious Adverse Device Effects (ASADE): is an effect which by its nature, incidence, severity or outcome has been identified in the anticipated AE's. No ASADEs have been identified in this case.

Imperial Clinical Trials Unit	ZODIAC STATISTICAL ANALYSIS PLAN – MAIN ANALYSIS	V1 17 th Jan 2024
-------------------------------	--	------------------------------

The assignment of causality and severity for adverse device effects should be made by the investigator responsible for the care of the patient using the definitions in the tables below (**Error! Reference source not found.** and **Error! Reference source not found.**).

Table 3: Causality definitions of adverse device effects

Causality	Definition
Unrelated	No evidence of any causal relationship
Unlikely	There is little evidence to suggest there is a causal relationship (e.g. the effect did not occur within a reasonable time after use of the device . There is another reasonable explanation for the effect(e.g. the patient's clinical condition, other concomitant treatment).
Possible	There is some evidence to suggest a causal relationship (e.g. because the effect occurs within a reasonable time after use of the device). However, the influence of other factors may have contributed to the effect (e.g. the patient's clinical condition, other concomitant treatments).
Probable	There is evidence to suggest a causal relationship and the influence of other factors is unlikely.
Definite	There is clear evidence to suggest a causal relationship and other possible contributing factors can be ruled out

Table 4: Severity definitions of adverse device effect

Severity	Definition
Mild	Awareness of effect but easily tolerated
Moderate	Discomfort enough to cause some interference with usual activity
Severe	Inability to carry out usual activity

5.5. Exploratory Variables

1. Proportion of patients achieving a decrease from baseline LDL-C level of more than 50% by Week 16 for LLT naïve patients
2. Percent change from baseline in LDL-C by Week 16 for LLT naïve patients
3. Percent change from baseline in non-HDL-C by Week 16 for LLT naïve patients
4. Percent change from baseline in HDL-C by Week 16 for LLT naïve patients
5. Percent change from baseline in triglycerides by Week 16 for LLT naïve patients
6. Percent change from baseline in total cholesterol by Week 16 for LLT naïve patients
7. Proportion of patients on combination therapy at Week 16 (for at least 4 weeks) achieving target LDL-C level <1.4 mmol/L (<55 mg/dL) and a decrease from baseline in LDL-C level of at least 50% by Week 16 for LLT naïve patients

Imperial Clinical Trials Unit	ZODIAC STATISTICAL ANALYSIS PLAN – MAIN ANALYSIS	V1 17 th Jan 2024
-------------------------------	--	------------------------------

8. Proportion of all patients achieving target LDL-C level <1.8 mmol/L (<70 mg/dL) by Week 16
9. Proportion of patients on combination therapies with three oral LLT or 1 injectable therapy plus one or more oral LLT
10. Proportion of patients with all-cause and CV mortality by Week 16
11. Proportion of patients with myocardial infarction, stroke/TIA, admission for CV reasons and revascularisations (CABG and/or angioplasty) by Week 16
12. Proportion of patients with goal achievement (LDL-C <1.4mmol/L or 55mg/dl by Week 16) in each trial arm stratified by institution setting (secondary/tertiary/mixed), country (UK/Spain/Italy) and by subpopulations defined by whether patients had experienced one or more CV events in the 2 years prior to admission.
13. LDL-C levels by 16 weeks among LLT-naïve (at ACS), monotherapy and combination therapy patients, within the DSS arm.
14. Quantitative evaluation as evaluated by the DSS Evaluation Questionnaire of the DSS by the clinicians at DSS sites

6. Estimands

6.1. Primary Estimand

In randomised trials there can be post-randomisation events that may have an impact on the outcome and thus the estimation of the effect of the intervention may be ambiguous if we do not consider these events. Therefore, we use the ICH E9 (R1) addendum on estimands and sensitivity analysis¹³ to define the primary estimand with its five attributes: treatment, population, variable, population-level summary, and handling intercurrent events.

The primary objective of the trial is to compare implementation of a DSS added to routine clinical care as compared with routine care without a DSS, to assess whether the availability of a DSS system in current practice increases the likelihood of initiation of combination therapy or escalation of LLT over a 16-week period. This is a pragmatic clinical trial and the primary estimand will be a treatment policy estimand that will answer the question whether DSS added to routine clinical care increases the likelihood of initiation of combination therapy or escalation of LLT over a 16-week period compared with routine care regardless of whether the prescriber uses the DSS for decision making.

The following attributes can describe the primary estimand (**Error! Reference source not found.**):

Imperial Clinical Trials Unit	ZODIAC STATISTICAL ANALYSIS PLAN – MAIN ANALYSIS	V1 17 th Jan 2024
-------------------------------	--	------------------------------

Table 5: Primary estimand attributes for the primary outcome

Estimand Attributes	Definition
Population	Adults admitted with ACS to hospital sites where subsequent study data follow up of the patients is carried out defined by ZODIAC inclusion and exclusion criteria
Treatment conditions	Experimental (DSS and SoC) versus control (SoC alone)
Outcome variables	Patients treated with combination therapy, or who receive escalated monotherapy, or escalated combination therapy, within 16 weeks of the index ACS (regardless of adherence i.e. use of the DSS by the prescribing physician for decision making)
Intercurrent events (and strategies to handle them)	Adherence to the DSS system (at participant level i.e. physician in DSS site does not use DSS) – treatment policy ¹ Patients who die are excluded from the analysis – principal stratum ²
Population Summary measure	Risk ratio adjusted for stratification variables (country and type of site)
Rationale for choosing estimand	The aim is to estimate the benefit of DSS vs SoC for patients with ACS if adopted as part of routine clinical care regardless of adherence to the DSS (as this reflects the pragmatic nature of the trial and real-world use). The outcome of patients who die during follow up is unknown. These patients are excluded from the analysis because the mortality rate is anticipated to be low in this population.

¹A treatment policy strategy considers the occurrence of the associated event as irrelevant, and participant data are analysed regardless.

² Principal stratum strategy includes only those subjects without the intercurrent event

6.2. Supplementary Estimand

A supplementary estimand (**Error! Reference source not found.**) using a principal stratum strategy will be used to assess whether the DSS added to routine clinical care increases the likelihood of initiation of combination therapy or escalation of LLT over a 16-week period compared with routine care in patients in whom the DSS is used by the prescribing physician for decision making.

A second, unblinded, statistician will perform this analysis using programming code prepared by the primary blinded study statistician.

Table 6: Supplementary estimand attributes for the primary outcome

Estimand Attributes	Definition
Population	Adults admitted with ACS to hospital sites where subsequent study data follow up of the patients is carried out defined by ZODIAC inclusion and exclusion criteria
Treatment conditions	Experimental (DSS and SoC) versus control (SoC alone)
Outcome variables	Patients treated with combination therapy, or who receive escalated monotherapy, or escalated combination therapy, within 16 weeks of the index ACS
Intercurrent events (and strategies to handle them)	Adherence to the DSS system (at participant level i.e. physician in DSS site does not use DSS) – principal stratum ¹ Patients who die are excluded from the analysis – principal stratum ¹
Population Summary measure	Risk ratio adjusted for stratification variables (country and type of site)
Rationale for choosing estimand	The aim is to estimate the benefit of DSS vs standard care for patients with ACS if adopted as part of routine clinical care in patients for whom the prescribing physician uses the DSS for decision making. The outcome of patients who die during follow up is unknown. These patients are excluded from the analysis because the mortality rate is anticipated to be low in this population.

¹ Principal stratum strategy includes only those subjects without the intercurrent event

Imperial Clinical Trials Unit	ZODIAC STATISTICAL ANALYSIS PLAN – MAIN ANALYSIS	V1 17 th Jan 2024
-------------------------------	--	------------------------------

7. Analysis Populations

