We define the primary outcome as missing for anyone who does not have full 16 week follow up, unless they have met the primary outcome prior to the time they are lost to follow up. All patients will be followed up and the primary outcome data will be collected unless the participant requests to withdraw from data collection. Missing data will be examined and quantified; this will include the time of withdrawal and tabulation for reasons for non-completion of study by country, site, and arms. Patterns of missingness and relationship between variables and outcome will be explored. The proportion of clusters (sites) with a missing individual outcome will be calculated and reported as the number of entire clusters with a missing outcome divided by the number of clusters randomised.

As mentioned in Section 4.8, some patients may have data reported at 24 weeks only. These data may be used, where appropriate, to derive or impute the LLT medication status at 16 weeks.

Although mixed models are valid under the missing at random (MAR) assumption, we will use the multilevel multiple imputation (MMI) method to impute values for individuals who have missing outcome data. Missing data can be related to the cluster level or at patient level. We define level 1 variables as those relating to the patient as X and Y and Z, and level 2 variables as those relating to the site as A and B.

Using the *JOMO package* in R with missing outcome data we can use an imputation model which is the same as the analysis model. The JOMO package allows imputation on a mix of multilevel continuous and categorical data.¹⁵ This method uses Markov chain Monte Carlo (MCMC) methods to impute missing values. We will run N imputations and combine the estimates using the mitools package. We will impute N datasets based on the percentage of participants with incomplete outcomes, where N is rounded to the nearest 10. A minimum of 5 imputation datasets will be used. We will include at patient level, intervention, outcome,

Imperial Clinical Trials Unit	ZODIAC STATISTICAL ANALYSIS PLAN – MAIN ANALYSIS	V1 17 th Jan 2024
-------------------------------	--	------------------------------

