8.10. Sensitivity Analysis

Two sensitivity analyses are planned for this study as below:

- A complete case analysis of the primary outcome will be undertaken as a sensitivity analyses. This will include all eligible and randomised patients whose outcomes are

Imperial Clinical Trials Unit	ZODIAC STATISTICAL ANALYSIS PLAN – MAIN ANALYSIS	V1 17 th Jan 2024
----------------------------------	--	------------------------------

available by 16 weeks. Patients in population will be analysed according to the randomised group allocated to the cluster (site) in which they are followed, either SoC or DSS.

- Full ITT analysis including patients who died and incorporating multiple imputation.

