12.4.2. Supplementary estimand

Table 24: Effect of DSS on proportion of patients initiated on combination therapy, escalation of monotherapy or escalation of combination therapy in patients for whom the prescribing physician used the DSS

Patients with primary outcome at 16 weeks	Trial arm		Adjusted Risk Ratio*	95% confidence interval
	DSS	Control		
N			x.xx	x.xx to x.xx
n (%)				

*adjusted for country, site type (secondary/tertiary care/mix of both) and study site

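### Both principal-stratum labels in the SAP describe exclusion on an observed event: Table 24 compares DSS users with effectively all controls, and the primary analysis drops patients who intensified before dying

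*SAP*

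**What the plan says.** SAP 6.1 (Table 5) and 6.2 (Table 6) both use the principal stratum label, and the Table 6 footnote defines it: "Principal stratum strategy includes only those subjects without the intercurrent event".

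*Supplementary estimand.* The intercurrent event is given as "Adherence to the DSS system (at participant level i.e. physician in DSS site does not use DSS) – principal stratum". The question is whether the DSS increases intensification "compared with routine care in patients in whom the DSS is used by the prescribing physician for decision making". The rationale row of Table 6 says the aim is to estimate the benefit of the DSS in those patients. The summary measure is a risk ratio adjusted for country and site type. Table 24 reports it with a DSS and a Control column, for the effect "in patients for whom the prescribing physician used the DSS".

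*Deaths.* Table 5 states: "Patients who die are excluded from the analysis – principal stratum". Two reasons are given: "The outcome of patients who die during follow up is unknown", and mortality is expected to be low. Section 8.4 excludes every death within 16 weeks from the primary analysis. The same section treats the outcome as missing without full 16-week follow-up, "unless they have met the primary outcome prior to the time they are lost to follow up". Under 5.2 the outcome is Yes if intensification occurs at any time, and it can be met as early as discharge. Section 8.10 adds as a sensitivity analysis: "Full ITT analysis including patients who died and incorporating multiple imputation". Mortality is tabulated by arm, and deaths stay in the time-to-event analysis until censored.

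**The concern.** Section 6.1 invokes ICH E9(R1). In that framework a principal stratum is a group fixed by potential event status under both allocations, for example patients for whom the tool would be used if it were available. Such patients exist in both arms but can be seen only in the DSS arm. Deleting observed non-users from one arm does not estimate an effect in that stratum, and the SAP names no method for identifying the corresponding control patients.

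Non-use is recorded patient by patient, and treatment choice remains with the clinician (4.2), so a clinician's use of the tool may be related to readiness to intensify. Table 24 could then show a benefit, or hide one, for reasons unrelated to the DSS, yet its stated aim invites a causal reading.

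For deaths, the primary analysis conditions on a post-randomisation event on the ground that the outcome is unknown. For a patient who intensified at discharge and later died, the outcome has been recorded.

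**Working it through.** **The plan's own figures.** The SAP gives no figure for DSS use or mortality. Section 4.5 supplies the design rates (5% SoC, 15% DSS) and the sample size, which reproduces. The design effect is 1 + (31 − 1) × 0.1 = 4. The unpooled two-proportion formula at 90% power gives 183.9 per arm, and 183.9 × 4 = 735.5, or 23.7 clusters of 31. That rounds up to 24 × 31 = 744. With 5% loss, 31/0.95 = 32.6, so 33 per site: 33 × 24 = 792 per arm and 1584 in all.

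**Who is compared in Table 24.** The event is defined only for DSS sites, so it removes no control patient. What remains is DSS-arm users against all controls, apart from deaths. This is an inference: the SAP does not say so outright, and Appendix D has no code for this estimand.

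**Risk ratio with no DSS effect.** Let u be the share of DSS-arm patients for whom the tool is used, and r the users'/non-users' ratio of underlying intensification rates. Both are assumptions. With overall rate p, the non-users' rate is p/(ur + 1 − u) and the users' rate is r times that. Against all controls at rate p:

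expected RR = r / (ur + 1 − u), whatever p is.

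| u | r = 0.5 | r = 1 | r = 2 | r = 3 |
|---|---|---|---|---|
| 0.9 | 0.91 | 1.00 | 1.05 | 1.07 |
| 0.7 | 0.77 | 1.00 | 1.18 | 1.25 |
| 0.5 | 0.67 | 1.00 | 1.33 | 1.50 |

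Example at p = 5%, u = 0.7, r = 2: non-users 0.05/1.7 = 2.94%, users 5.88%, arm total 0.7 × 5.88 + 0.3 × 2.94 = 5.0%. The true RR is 1.00; users against controls gives 5.88/5 = 1.18. The upper limit is 1/u.

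**Risk ratio at the design effect.** Take 15% against 5% overall, u = 0.7, and assume no effect in non-users.
- r = 2: users under the DSS (0.15 − 0.3 × 0.0294)/0.7 = 20.2%. RR in would-be users 20.2/5.88 = 3.43; planned comparison 20.2/5 = 4.03.
- r = 0.5: non-users 0.05/0.65 = 7.69%, would-be users without the DSS 3.85%, users under the DSS (0.15 − 0.3 × 0.0769)/0.7 = 18.1%. RR in would-be users 4.71; planned comparison 3.63.

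So the bias can run either way.

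**Deaths.** Mortality of 1%, 2% and 5% (assumed) removes 1584 × 0.01 = 16, 32 and 79 patients. If they had intensified at the design rates, the known positive outcomes dropped are 792 × d × (0.05 + 0.15) = 1.6, 3.2 and 7.9. The design rates were set for combination therapy, whereas the outcome also counts escalation, so the number could be larger: at an assumed 30% in both arms, 15.84 × 0.30 = 5 to 79.2 × 0.30 = 24. Early deaths leave less time to intensify, which pulls the other way.

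**The full ITT analysis.** A patient who dies without intensifying lacks 16-week follow-up, so the missing-outcome rule in 8.4 makes the outcome missing, and 8.10 would impute it. That fills in prescribing after death.

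**The case against.** *On DSS use.* Non-use is handled by treatment policy in Table 5. A reader might infer that selection of users biases the primary risk ratio; the documents do not support that. Table 24 names its population and does not claim to be the overall effect. Use may be nearly complete: the schedule in 4.8 makes it optional only after baseline, and staff are asked to use the tool at follow-up. At 95% use the expected RR with no effect is only 2/1.95 = 1.03 for r = 2 and 3/2.9 = 1.03 for r = 3. All of this stands as a limit on size. It does not make exclusion of observed non-users an estimator of the stated target, and the rationale row still presents the result as the benefit of the DSS.

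*On deaths.* The rule in 8.4 speaks of loss to follow-up, and death has its own rule, so there is no formal clash between the two. Low mortality is a second reason. If deaths and decedents' rates are alike in both arms, the RR does not move. Even with 4% DSS and 2% SoC deaths, none intensified, counting them as not met gives (0.15 × 0.96)/(0.05 × 0.98) = 0.144/0.049 = 2.94 against 3.00. Deaths are also covered by the full ITT analysis, the mortality table and the time-to-event analysis. A reader might infer that the primary result is materially distorted; nothing here shows that. What remains is a reason for exclusion that is wrong for some patients.

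*On a complier estimate as the remedy.* It requires that allocation has no effect on non-users, yet whole DSS sites are trained (4.1) and clinicians may carry what they learn to other patients. It can also be unstable. Its denominator is [SoC risk − (1 − u) × non-users' risk]/u. At 5% SoC risk, 60% use and 15% risk in non-users, this is (0.05 − 0.06)/0.6, which is negative. With non-users at 5% it is 0.05, with a standard error of about 0.03 at ICC 0.1 and 744 per arm. This objection stands, so the complier analysis should be optional.

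**Conclusion.** The concern holds. Both uses of the principal stratum label describe exclusion on an observed post-randomisation event.

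The more serious part is confined to the supplementary estimand. If use is related to readiness to intensify, Table 24 is biased: about 1.05 to 1.50 with no true effect, for 90% to 50% use and users two to three times as likely to intensify; below 1 if users are less likely; negligible if use is near complete or unrelated to readiness. Use share and rate ratio are assumptions, and the retention of all surviving controls is inferred from how the event is defined. A reader might conclude that Table 24 must favour the DSS; the documents give no basis for a direction.

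The death part touches the primary analysis but is small: about 2 to 8 known positive outcomes at 1% to 5% mortality and the design rates. It is worth correcting because the stated reason is wrong for those patients, and because the sensitivity analysis as worded would impute prescribing after death.

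**What to change.** **Supplementary estimand (6.2, Tables 6 and 24).** State what counts as DSS use for a patient, including whether baseline use alone suffices. Relabel the analysis as a per-protocol, non-causal description, and remove the wording that presents it as the benefit of the DSS in users. If a causal effect in would-be users is wanted, add an optional complier risk ratio using site allocation as the instrument: adjusted for country and site type, with a site-level bootstrap interval, an explicit assumption that allocation and site training do not affect non-users, and a warning that it may be unstable at low control risk.

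**Deaths (6.1, 7.1, 8.4, 8.10).** Count intensification before death as met and death without intensification as not met (a while-alive definition), and keep these patients in the primary analysis. Do not impute outcomes after death in the full ITT analysis. Keep the analysis that excludes deaths as a sensitivity analysis. Section 8.4 extends the exclusion to similar secondary outcomes, so say whether the new rule applies there too.

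**Cost.** SAP wording and a small change to the outcome derivation; the deaths change needs no new data. The optional complier analysis needs a short extra programme and is likely to give a wider interval than the users-against-controls comparison. The changes should be made before the data are unblinded.

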7.1. Intention To Treat Population

As we considered principal stratum strategy to handle death, the primary analysis will be undertaken on an ‘modified intention-to-treat’ (mITT) basis. This will allow for the inclusion of all eligible and included patients through use of multiple imputation (Section 9.1 and 9.2) after excluding patients who died. Patients in the mITT population will be analysed according to the randomised group allocated to the cluster (site) in which they are followed, either SoC or DSS, irrespective of noncompliance.

We will also undertake two sensitivity analyses on full ITT population and on those with complete cases (i.e. complete outcome data).

7.2. Safety Population

As in this trial all patients will be treated only in line with SoC, the treating physicians at study sites will report any Adverse Drug Reactions (ADRs)/ Adverse Events (AEs) in routine ways in accordance with the guideline on Good Pharmacovigilance Practice (GVP) for all medications trial patients are taking during the course of the trial. This is not a Clinical Trials of Investigational Medicinal Product (CTIMP), therefore no Serious Adverse Events in relation to the licensed medicines are being collected.

Device deficiencies will be captured in those patients who are at a study site using DSS only. Device deficiencies include malfunctions, user errors and inadequacy in the software supplied by the manufacturer.

Imperial Clinical Trials Unit	ZODIAC STATISTICAL ANALYSIS PLAN – MAIN ANALYSIS	V1 17 th Jan 2024
-------------------------------	--	------------------------------

8. Statistical Analysis

